During cooling, Tty will be monitored utilizing infrared technology as a non-invasive estimate of brain temperature. A standard low-temperature rectal temperature probe will also be inserted to help assure a reasonable degree of total body cooling for EPR. Cooling will continue until Tty is <10°C and rectal temperature is <30°C. At this point, low flow CPB (10 ml/kg/min) will continue if possible. If not, circulation will be arrested until hemostasis has been secured.

The subject will be transported to the operating room (if not already in the operating room) for resuscitative surgery as soon as it is feasible. During the operation, if necessary, additional cannulae (FDA-approved) may be placed for CPB. The exact placement will depend upon the subject's injuries. A standard aortic arch approach may be appropriate. This will allow repair of the initial aortotomy.

The operative approach will be focused on damage control. Arterial bleeding will be managed with ligation or vascular repair. Venous bleeding will mostly be managed with packing, though direct repair or ligation may be needed. Contamination by enteric contents will be managed by rapid resection and bowel stapling, plus irrigation of the peritoneal cavity. All surgical fields will remain open for observation during reperfusion and rewarming to assure hemostasis. The abdomen and thorax are frequently packed and left open in these circumstances.

Although EPR should not be initiated in subjects with non-survivable injuries, it is possible that the severity of the injuries may not be evident until the patient has been cooled and undergoes operative exploration. If, at this time, non-survivable injuries are identified, the attending surgeon may elect not to continue resuscitative efforts.

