Thoracotomy tray and standard trauma resuscitation equipment and supplies will be available per standard care of trauma patients. Specific equipment for this study that will be readily available in the ED will include: large volumes of ice-cold saline in a refrigerator (30 liters stored in a designated refrigerator for this trial), arterial and venous cannulae (various sizes and types), appropriate tubing, CPB pump, and hollow-fiber membrane oxygenator/heat exchangers. This equipment will be stored in a storage area near the trauma resuscitation rooms in the Emergency Department. It will be labeled at the site with the following warning: "CAUTION -Investigational Device/Drug. Limited by Federal (or United States) law to investigational use."

Concurrent Control Group:

We will collect data on concurrent patients who are appropriate candidates for EPR, but do not have EPR initiated because the team is not available. These data will include specifics of resuscitative efforts and the same outcome parameters as the EPR group. Per the request of the FDA, 10 concurrent control subjects will be entered and a detailed report will be submitted to the FDA prior to any further subject enrollment.

Historical Control Group:

Because of concern that bias may influence the selection of subjects who receive EPR, thus affecting the concurrent control group, outcome information regarding similar patients in the trauma registry of the respective institutions (Level I trauma centers) will be obtained. The most recent 100 patients who had undergone an ED thoracotomy will be reviewed. Additional subjects may be required in order to obtain at least 10 subjects who would have met criteria for entry into the study.

Consent:

Due to the emergency nature of the traumatic event and the need for immediate resuscitation, including initiation of EPR, this study must be performed under the Exception from Informed Consent for emergency research as outlined in FDA regulation 21CFR50.24. Once the subject has been stabilized, consent for continued participation in the study for collection of data and long-term follow-up, will be obtained from the subject's legal authorized representative (LAR). In addition, consent for follow up will be obtained for survivors in the control group. (See section X below for additional information regarding the exception from consent conditions, request, and justification.)

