Renal (serum creatinine - µmol/l)	< 1.1	1.2-2.3	2.4-3.9	4.0-5.6	>5.7
Hepatic (serum bilirubin - µmol/l)	< 1.1	1.2-3.5	3.6-7.1	7.2-14.1	>14.2
Cardiovascular (PAR*)	< 10.0	10.1-15.0	15.1-20.0	20.1-30.0	>30.0
Hematologic (platelet count –x 10 ⁻³)	>120	81-120	51-80	21-50	< 20

Primary objective

To demonstrate better survival to hospital discharge without major disability (Glasgow Outcome Scale-Extended >5) after resuscitation with EPR in exsanguinating trauma patients, compared to concurrent or historic control patients.

Secondary objective(s)

To examine the feasibility and safety of rapidly inducing profound cerebral hypothermia for EPR in exsanguinating trauma patients.

To examine 28-day survival, 6 and 12 -month neurologic functional outcome (Glasgow Outcome Score Extended [GOSE]) and SF-36, and the development of multiple organ dysfunction syndrome (MODS) in the EPR group, as compared to a concurrent control group.

Specific complications related to the implementation of EPR and CPB, such as vascular injuries, will be identified.

Data and Safety Monitoring Board.

This study will be monitored by a Data and Safety Monitoring Board (DSMB), which will include researchers with experience in resuscitation research from institutions not involved in the conduct of this clinical trial. At least one member of the DSMB will be a cardiothoracic surgeon.

At a minimum, the DSMB will be convened by teleconference or in person at least yearly. For the first 5-10 subjects enrolled in the trial (both EPR and control groups), the DSMB and the investigators will discuss each case by teleconference contemporaneously (within 30 days of subject enrollment). The DSMB will review each report submitted by the investigators to the FDA.

The DSMB will have the responsibility of making recommendations to the investigators and FDA regarding:

· Enrollment criteria, including inclusion and exclusion of subjects

- Technique used for induction of EPR and CPB for reperfusion
- Post-resuscitation mild hypothermia
- Outcome evaluations
- Patient safety
- Informed consent
- Performance of individual centers

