The goal will be to enroll 10 subjects that undergo EPR and 10 concurrent control subjects. A detailed report will be filed with the FDA after the first 5 subjects in each group have been discharged or have expired. A final report will be filed after the hospital courses of 10 subjects in each group have been completed. All interim and outcome reports from the DSMB will also be sent to the USAMRMC ORP HRPO.

Outcome data and data analysis

Survival to hospital discharge without major disability, MODS scores, survival at 28 days, GOSE and SF-36 (at 6 and 12 months) will be compared between groups. Complications felt to be possibly or definitely associated with of the EPR technique will be specifically recorded. As with any cardiac arrest resuscitation trial, there is a risk that a subject will survive with a poor neurologic outcome (e.g., comatose, vegetative). Based on the current literature for survivors of cardiac arrest from trauma with standard card, this risk is small.

The decision to proceed with further clinical investigation of the EPR technique will depend upon the frequency of associated complications (in relation to the high risk of death and morbidity secondary to the original injuries) and lack of inferiority to standard care with regard to the secondary endpoints. Based on information learned during the course of the study, the entry criteria may be revised in order to select subjects most likely to benefit from the intervention. The technique for EPR may also be revised. Evaluating these new criteria or techniques may justify further investigation. If, despite revisions of entry criteria and technique, survival appears to be no better than (or worse than) standard care, the study could be stopped. The FDA, ORP HRPO, and reviewing IRBs will be notified of such revisions prior to their implementation.

VIII. INCLUSION / EXCLUSION CRITERIA

Inclusion criteria

Subjects must meet all of the following inclusion criteria:

- Penetrating trauma with clinical suspicion of exsanguinating hemorrhage
- Age 18-65
- At least 1 sign of life at the scene (pulse, respiratory efforts, spontaneous movements, reactive pupils)
- Loss of pulse <5 min prior to ED arrival or in the ED or operating room
- Thoracotomy performed without immediate return of a palpable pulse in the carotid arteries after clamping the descending thoracic aorta

Exclusion criteria.

Subjects will be excluded for any of the following:

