- No signs of life for greater than 5 min prior to the decision to initiate EPR. This time frame is defined as the time from loss of pulse to the decision to switch to EPR.
- Age is >65 years or <18
- Obvious non-survivable injury
- Suggestion of traumatic brain injury, such as significant facial or cranial distortion
- Electrical asystole
- Rapid external assessment of the injuries suggests massive tissue trauma involving multiple body regions (for example, a crushed limb, distorted chest anatomy, or pelvic instability).

Pregnancy

- Prisoners
- Those with aortic arch injury that would preclude flush should be excluded from study participation.
- Active Military personnel

Based on clinical experience and published data, we believe that the most appropriate candidates for EPR would be subjects who have suffered a cardiac arrest from trauma, presumably from exsanguination, and do not respond to standard resuscitative efforts, including thoracotomy in the ED or operating room. Because of the need to conduct this study under the exception from informed consent, adults (>18 yo) will be included. To include subjects in this feasibility trial with the greatest potential for benefit, we will only include subjects with penetrating trauma. Subjects must be in cardiac arrest in the ED or operating room, as documented by the absence of a pulse in the femoral and carotid arteries. Standard resuscitation would include rapid fluid resuscitation and a thoracotomy with right tube thoracostomy. Subjects would become eligible for EPR if they do not respond immediately to these maneuvers and the injuries cannot readily be repaired via the thoracotomy (e.g., a stab wound to the heart for which the tamponade can readily be released and the wound quickly closed).

A checklist (Appendix A) will be utilized to guickly determine subject eligibility.

Subjects known to be prisoners upon admission will be excluded from the study. But if a subject is taken into custody after being enrolled in the study, we will continue to collect data (includes medical record review and review of their vital status).

IX. SUBJECT RECRUITMENT & SCREENING

Screening procedures

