The decision to enroll subjects into this trial will have to be made promptly by the trauma team resuscitating the subject. Information available to them will include the mechanism of injury, time from injury and paramedic arrival to ED arrival, physical examination for signs of life (pulse, breathing, spontaneous movements, reactive pupils), cardiac rhythm, and response to standard resuscitative efforts. This information will be available from Medic Command and the paramedics who transport the subject. Since time is of the essence, little more information may be available. The most important information for screening will be the condition of the subject upon arrival in the ED or operating room and the response to the standard resuscitative efforts, i.e., with either no or only transient restoration of pulse. No other screening procedures will be performed.

The number of subjects in this initial feasibility trial will be 20 (10 EPR and 10 concurrent control). After review of these subjects by the investigators, DSMB, FDA, and ORP-HRPO, a decision will be made to either discontinue the study, proceed with another cohort of subjects with revised inclusion criteria or EPR technique, or consider a randomized, pivotal trial.

X. INFORMED CONSENT PROCESS

This clinical study qualifies for the "Exception from informed consent for emergency research" outlined in the FDA regulation at 21 CFR Section 50.24. Listed below are the respective regulatory criteria and corresponding justifications for the applicability of this clinical study.

(1) The human subjects are in a life-threatening situation, available treatments are unproven or unsatisfactory, and the collection of valid scientific evidence, which may include evidence obtained through randomized placebo-controlled investigations, is necessary to determine the safety and effectiveness of particular interventions.

These potential subjects are clearly in a life-threatening situation with unsatisfactory available treatments, as evidenced by a <10% chance of survival based on current literature. The collection of valid scientific evidence is necessary to determine the safety and effectiveness of EPR.

- (2) Obtaining informed consent is not feasible because:
 - (i) The subjects will not be able to give their informed consent as a result of their medical condition;
 - (ii) The intervention under investigation must be administered before consent from the subjects' legally authorized representatives is feasible; and

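### Historical controls are picked from records that already show the outcome, while EPR eligibility is settled at the bedside, so hindsight can shape the benchmark

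*Protocol*

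**What the plan says.** **Primary objective (section VII).** "To demonstrate better survival to hospital discharge without major disability (Glasgow Outcome Scale-Extended >5) after resuscitation with EPR in exsanguinating trauma patients", with concurrent or historic patients as the comparator. The planned size is 10 EPR subjects and 10 concurrent controls, not randomised.

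**EPR subjects.** Section IX (Screening procedures): "The decision to enroll subjects into this trial will have to be made promptly by the trauma team resuscitating the subject". Section X puts the window for trying standard care, judging it failed and starting EPR at about 5 minutes. Section VIII adds: "A checklist (Appendix A) will be utilized to guickly determine subject eligibility".

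**Historical controls (section VII, Historical Control Group).** These are added because selection of EPR subjects might bias the concurrent group. Outcome information comes from the institutions' trauma registries, and the latest 100 ED thoracotomies are reviewed. The frame may then grow: "Additional subjects may be required in order to obtain at least 10 subjects who would have met criteria for entry into the study". The text does not say what the person judging eligibility may see, how far or in what order the frame may be extended, or whether all qualifiers or only 10 are used.

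**Concurrent controls (section VII, Concurrent Control Group).** These are "concurrent patients who are appropriate candidates for EPR, but do not have EPR initiated because the team is not available". Who identifies them, and when, is not stated. The Personnel paragraph of the same section bars enrolment when the trained team is absent.

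**Criteria that need judgement.** Section VIII requires "Thoracotomy performed without immediate return of a palpable pulse" in the carotids after aortic clamping, excludes obviously non-survivable injury, and describes candidates as those whose injuries cannot readily be repaired through the thoracotomy. On hidden injury in EPR subjects, section VII (Clinical protocol) accepts that "it is possible that the severity of the injuries may not be evident until the patient has been cooled and undergoes operative exploration".

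**The concern.** The two sides of the comparison are admitted with different information. The trauma team chooses EPR subjects without knowing how the case will end. Historical controls are chosen by someone working from a completed record, in the source that holds the outcome.

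Four criteria leave room for hindsight in such a review:

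- **Immediate return of pulse.** No time limit is given, and every survivor regained a pulse at some point. A known survivor is easily read as a responder and judged ineligible, which lowers control survival.
- **Readily repairable injury.** Survival suggests that the injury could be repaired, which pushes the same way.
- **Obvious non-survivable injury.** Operative or autopsy findings can make an injury look obvious afterwards. Excluding such deaths raises control survival, while an EPR subject with the same hidden injury stays in.
- **The 5-minute limit.** It runs from loss of pulse to the decision to switch to EPR. No historical control ever had that decision, so its end point must be reconstructed.

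The historical group exists to answer a worry about selection bias. If its own selection can depend on the outcome, it cannot do that job well.

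**Working it through.** The protocol states no alpha, power or target effect; 10 and 10 is a goal linked to an FDA request. There is no planned figure to reproduce, so what follows is a sensitivity check.

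**Inputs (protocol, section VII, Rationale).** Survival after ED thoracotomy: 7% overall, 9% for penetrating trauma, 12% with and 3% without signs of life on arrival. More than 90% of survivors had normal neurologic outcome, so survival is used here as an approximation to the primary endpoint.

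**Step 1: how many survivors carry the benchmark.** With n = 10, expected survivors = 10p and P(none) = (1 − p)^10.

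| p | Expected survivors | P(none) |
|---|---|---|
| 3% | 0.3 | 74% |
| 7% | 0.7 | 48% |
| 9% | 0.9 | 39% |
| 12% | 1.2 | 28% |

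Swapping one of 10 controls for a patient with the other outcome moves the rate by 1/10 = 10 points, more than the whole 7% benchmark.

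**Step 2: size of a selection effect in either direction.** Let s be the share judged ineligible through hindsight (an assumption; the documents give no value).

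- Survivors excluded: rate = p(1 − s) / [p(1 − s) + 1 − p]. At p = 7% and s = 25%, 50%, 75%: 5.3%, 3.6%, 1.8%.
- Deaths excluded: rate = p / [p + (1 − p)(1 − s)]. At p = 7% and the same s: 9.1%, 13.1%, 23.1%.
- At p = 9% and s = 50%: 4.7% or 16.5%.

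**Step 3: chance that EPR looks numerically better when it has no effect.** Let X be EPR survivors out of 10 and Y control survivors out of m, both at 7%. P(X≥1) = 0.516, P(X≥2) = 0.152, P(X≥3) = 0.028.

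- m = 10, unselected. P(Y = 0, 1, 2) = 0.484, 0.364, 0.123. P(X > Y) = 0.484×0.516 + 0.364×0.152 + 0.123×0.028 + a negligible remainder ≈ 0.31.
- m = 12, unselected. P(Y = 0, 1, 2, 3) = 0.419, 0.378, 0.157, 0.039. One survivor in 12 (8.3%) is already beaten by one in 10, so P(X/10 > Y/12) = 0.419×0.516 + 0.378×0.516 + 0.157×0.152 + 0.039×0.028 ≈ 0.44.
- All control survivors removed. P(X≥1) = 1 − 0.93^10 = 0.52.

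The gap between 31% and 44% comes from how ties fall with 10 and 12 controls, not from bias.

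**Step 4: can one control alter a conclusion?** The protocol names no test. With a two-sided Fisher exact test, 5/10 against 0/10 gives p = 0.033 and 5/10 against 1/10 gives p = 0.141. One reclassified control crosses the usual 0.05 line.

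**The case against.** The protocol has some protection. The starting pool is the most recent 100 cases, not a hand-picked set. Age, mechanism and asystole are objective. A careful reviewer would see that an injury found only at operation was not obvious, and that later survival does not prove immediate pulse return. All of this limits the bias. It does not remove the discretion in the remaining criteria, and nothing tells the reviewer to set later findings aside.

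A reader might infer that concurrent controls, too, are chosen after the outcome is known. The documents do not support that. Section IX describes a prompt decision by the resuscitating trauma team and counts the 10 concurrent controls as trial subjects. Appendix A is a rapid checklist, and the trauma team could complete it even when the EPR team is absent. Section XII requires a case report form in both arms, and the DSMB discusses the first 5 to 10 subjects, controls included, within 30 days. What stands is that timing and decision-maker are unstated and that the Personnel paragraph conflicts with this group's definition. Neither safeguard clearly covers the historical controls.

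A reader might also be drawn to a starker example: 2 survivors among 12 eligible controls, both recoded to leave 0/10, which moves the chance that EPR looks better from 15% to 52%. That starts from an unusually good control result. At 7%, two or more survivors in 12 occurs only about 20% of the time (1 − 0.419 − 0.378). Averaged over control sampling, the starting chance is 31% or 44%.

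Finally, this is a safety and feasibility study. Further work depends on complications and secondary endpoints, and abstraction details could sit in a separate document. That lowers the stakes. Even so, the primary objective is comparative, and the protocol itself sets how controls are found.

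**Conclusion.** The point holds for the historical controls. Their eligibility is judged from records that also hold the outcome and later findings, against partly subjective criteria, in a frame that can be extended without limit. EPR eligibility is fixed at the bedside. The plan permits outcome-influenced selection; it does not show that this will happen, and the direction cannot be determined.

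The possible effect is large relative to the benchmark: about 10 points per reclassified control, against an expected rate of 3% to 12%. At a common 7%, the worst case favouring EPR takes the chance of a numerical advantage from about 31% (10 controls) or 44% (12 controls) to 52%. Excluding deaths instead would work against EPR. These figures assume independent binomial outcomes, the protocol's literature rates, and survival standing in for the primary endpoint.

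For the concurrent controls, the finding is only that the process is unstated and that two paragraphs of section VII must be reconciled. The change is worth making because it is cheap and protects the comparator of the primary objective.

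**What to change.** **Historical controls.** Add a short paragraph to section VII:

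1. Take consecutive ED thoracotomies, starting with the most recent 100. If fewer than 10 qualify, extend only in consecutive order.
2. Abstract only information available up to the point at which EPR would have been considered. Withhold outcome, disposition and later operative findings. State how that point is located in a patient for whom EPR was never an option.
3. Complete the Appendix A checklist from that abstract and lock it.
4. Include every patient who qualifies.
5. Only then open the outcomes, and report how many records failed each criterion.

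**Concurrent controls.** State who determines eligibility and when. Have the treating trauma team complete a time-stamped Appendix A checklist at the resuscitation; where that is not done, use the same masked, locked abstraction. Reconcile the Personnel paragraph with the Concurrent Control Group paragraph.

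**Cost.** Some hours of staged abstraction by existing staff for about 100 records. No sample-size figure changes. Masking will be imperfect where early notes hint at the outcome.

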Title 10 United States Code 980 states that "Funds appropriated to the Department of Defense may not be used for research involving a human being as an experimental subject unless- (1) the informed consent of the subject is obtained in advance; or (2) in the case of research intended to be beneficial to the subject, the informed consent may be obtained from a legal representative of the subject."

Even though there is intent to benefit patients enrolled in this study, the informed consent of the LAR is likely not going to be possible to secure in advanced, hence a waiver of 10 USC 980 will be requested.

XI. DATA COLLECTION, ANALYSIS and COORDINATION

Data collection

Procedures to assess efficacy:

The primary outcome variable will be survival to hospital discharge without major disability (Glasgow Outcome Scale-Extended >5) after resuscitation with EPR in exsanguinating trauma patients, compared to concurrent or historic control patients. the ability (feasibility) and safety of inducing EPR. Secondary outcomes will include: 1) the feasibility and safety of rapidly inducing profound cerebral hypothermia for EPR in exsanguinating trauma patients, 2) 28-day survival, 3) 6 and 12-month neurologic functional outcome (Glasgow Outcome Score Extended [GOSE]) and SF-36, and 4) the development of multiple organ dysfunction syndrome (MODS) (see Table: Multiple Organ Dysfunction Score) in the EPR group, as compared to a concurrent control group and historical controls.

Once the EPR subject has been rewarmed and, if possible, weaned from CPB, there will be no additional invasive procedures performed on the subject for the specific purpose of the research study. The subject will continue to undergo standard medical procedures as indicated for the clinical care of his/her trauma injury.

For subjects in both arms of the study, the medical record will be utilized to determine the occurrence of multiple organ system dysfunction or death.

The MODS Score (Table) will be utilized to quantify the level of organ system dysfunction.

Neurologic functional outcome will be assessed in survivors using the GOSE and SF-36 at 6 and 12 months. If the subject is discharged from the hospital prior to either of these dates, GOSE information will be obtain via telephone calls to the subject or the subject's LAR.

			Score		
Organ system	0	1	2	3	4
Respiratory (PO ₂ /FiO ₂)	>300	226-300	151-225	76-150	< 75

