The primary outcome measure is survival to hospital discharge without major disability (Glasgow Outcome Scale-Extended ≥5). Secondary outcomes include survival at 28 days, GOSE and SF-36 (at 6 and 12 months) will be compared between groups. Complications felt to be possibly or definitely associated with the EPR technique will be specifically recorded. The decision to proceed with further clinical investigation of the EPR technique will depend upon the frequency of associated complications (in relation to the high risk of death and morbidity secondary to the original injuries) and lack of inferiority to standard care with regard to the secondary endpoints. Based on information learned during the course of the study, the entry criteria may be revised in order to select subjects most likely to benefit from the intervention. The technique for EPR may also be revised. Evaluating these new criteria or techniques may justify further investigation. The FDA, ORP HRPO, and reviewing IRBs will be notified of such revisions prior to their implementation.

Data Coordination

Data will be collected at each site on the attached case report form (Appendix C). The information will be transmitted via a secure website to the data collection center at the University of Pittsburgh. Each subject will be assigned a unique code for the study. No patient identifiers will be transmitted to the data center. Links to personal identifiers will be maintained in locked filing cabinets at each site.

XII. LABELING & STORAGE OF DATA & SPECIMENS

A Case Report Form (CRF, see Appendix B) will be completed for each subject (both arms) enrolled into the clinical study. The responsible investigator for each study site will review, approve and sign/date each completed CRF; the investigator's signature serving as attestation of the investigator's responsibility for ensuring that all clinical and laboratory data entered on the CRF are complete, accurate and authentic.

The CRF will be electronically transmitted to the data center at the University of Pittsburgh without patient identifiers.

The investigator-sponsor and study site investigators will maintain records in accordance with Good Clinical Practice guidelines to include:

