Serious adverse effect. Any adverse effect that results in any of the following outcomes: death, a life-threatening adverse effect, inpatient hospitalization or prolongation of existing hospitalization, a persistent or significant disability/incapacity, or a congenital anomaly/birth defect.

Hospitalization shall include any initial admission (even if less than 24 hours) to a healthcare facility as a result of a precipitating clinical adverse effect; to include transfer within the hospital to an intensive care unit. Hospitalization or prolongation of hospitalization in the absence of a precipitating, clinical adverse effect (e.g., for a preexisting condition not associated with a new adverse effect or with a worsening of the preexisting condition; admission for a protocol-specified procedure) is not, in itself, a serious adverse effect.

Unexpected adverse effect. Any adverse effect, the frequency, specificity or severity of which is not consistent with the risk information described in the clinical study protocol(s) or elsewhere in the current IDE application, as amended.

Unanticipated adverse device effect. Any serious adverse effect on health or safety or any lifethreatening problem or death caused by, or associated with, a device, if that effect, problem, or death was not previously identified in nature, severity, or degree of incidence in the investigational plan or IDE application (including a supplementary plan or application), or any other unanticipated serious problem associated with a device that relates to the rights, safety, or welfare of subjects.

Anticipated risks of the EPR procedure itself include:

- 1. Injuries to the vascular structures that are cannulated (aorta, femoral vessels, right atrium)
- 2. Air or clot embolism
- 3. Hemolysis
- 4. Coagulopathy

Eliciting adverse effect information.

For surviving subjects (both arms), the research coordinator will visit the subject daily for two weeks to evaluate for any adverse events that were not recorded in the subject's medical record. Surviving subjects will also be routinely questioned about adverse effects at the 28 day and 6 and 12 month follow-up interviews.

Recording and assessment of adverse effects.

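### The primary outcome needs a GOSE rating at hospital discharge, but the protocol schedules GOSE only at 6 and 12 months

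*Protocol*

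**What the plan says.** The primary outcome is stated in Section VII (Outcome; Primary objective) and again in Section XI (Procedures to assess efficacy; Outcome data and data analysis). Section XI puts it this way: "The primary outcome variable will be survival to hospital discharge without major disability", followed by a GOSE cut-off. The comparison is with concurrent or historical controls.

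Section XI then sets out how outcomes are collected:

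- **GOSE:** "Neurologic functional outcome will be assessed in survivors using the GOSE and SF-36 at 6 and 12 months". Subjects discharged before either date are telephoned.
- **Medical record:** for both arms, "the medical record will be utilized to determine the occurrence of multiple organ system dysfunction or death".
- **Status of the later GOSE:** "Secondary outcomes include survival at 28 days, GOSE and SF-36 (at 6 and 12 months) will be compared between groups".

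Two further places bear on timing and source. Section VII (Data and Safety Monitoring Board) ties the FDA reports to hospital course: "A detailed report will be filed with the FDA after the first 5 subjects in each group have been discharged or have expired", and then "A final report will be filed after the hospital courses of 10 subjects in each group have been completed". Section VII (Historical Control Group) obtains "outcome information regarding similar patients in the trauma registry of the respective institutions".

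**The concern.** A subject who leaves hospital alive cannot be classed as success or failure on this endpoint without a GOSE at that time. The collection schedule provides none. If sites follow the protocol as written, the primary outcome is known for everyone who dies in hospital and unknown for anyone discharged alive before month 6.

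Two things are at stake. First, the FDA reports may have to present the primary comparison without the rating that decides it. Second, if ratings are improvised to fill the gap, they may be made differently in the EPR, concurrent and historical groups. Part of any difference between groups would then reflect how the outcome was rated.

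**Working it through.** The protocol gives no power, alpha or effect size, so there is no planned figure to reproduce. The check compares the endpoint with the collection schedule and then sizes the gap.

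**Step 1. Is a discharge GOSE scheduled anywhere?**

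| Place in the protocol | What it provides | GOSE at discharge? |
|---|---|---|
| VII, Outcome | Primary outcome at discharge; GOSE at 6 months as secondary | Required by the definition, not scheduled |
| VII, Secondary objectives | GOSE at 6 and 12 months | No |
| VII, Outcome data and data analysis | Discharge endpoint listed separately from 6- and 12-month GOSE | Required, not scheduled |
| XI, Procedures to assess efficacy | GOSE at 6 and 12 months, by telephone if already discharged | No |
| XI, same section | Medical record for organ dysfunction or death | Not named |
| XI, Outcome data and data analysis | Discharge endpoint primary; 6- and 12-month GOSE secondary | Required, not scheduled |
| XVII, Eliciting adverse effect information | Daily visits for two weeks; interviews at 28 days, 6 and 12 months, all for adverse effects | No |
| Appendix B, as readable | GOSE field in the long-term follow-up block | None visible (weak evidence) |

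The Section XVII contacts cannot fill the gap as written. For example, "the research coordinator will visit the subject daily for two weeks to evaluate for any adverse events", with no GOSE assigned. The 6-month value cannot stand in either, because Section VII lists the discharge endpoint and the later GOSE as different outcomes.

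**Step 2. Who is affected?** In-hospital death is GOSE 1 and so a failure under any reading of the cut-off. The gap therefore falls only on live discharges.

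**Step 3. Size.** Inputs: n = 5 per group (first FDA report) and n = 10 per group (final report), both from Section VII. Let k be the number of live discharges without a rating, with all other subjects dead in hospital. The protocol gives no value for k, so it is an assumption. The group's success rate is then known only to lie between 0/n and k/n.

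- One subject moves the rate by 1/5 = 20 points at the first report and by 1/10 = 10 points at the final report.
- n = 5: k = 1 gives 0–20%; k = 2 gives 0–40%.
- n = 10: k = 1 gives 0–10%; k = 2 gives 0–20%; k = 3 gives 0–30%.
- Historical controls (at least 10 subjects): at most 10 points per subject.

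**Step 4. How many survivors might there be under standard care?** The Section VII rationale cites survival of 7% overall and 9% in penetrating trauma. Section X states under 10%, so 10% serves as a ceiling. For 10 controls, the expected number of survivors is 10p and the chance of at least one is 1 − (1 − p)^10.

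| p | Expected survivors | Chance of at least one |
|---|---|---|
| 0.07 | 0.7 | 0.52 |
| 0.09 | 0.9 | 0.61 |
| 0.10 | 1.0 | 0.65 |

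One unrated survivor could therefore be the control group's entire possible success count.

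**The case against.** The strongest reply is that this is an omission and not a contradiction. The sentence on 6 and 12 months puts the secondary outcome into practice and does not say that GOSE is rated at no other time. The primary outcome carries its own instrument and time point, and reports triggered by discharge fit an intended discharge rating. Section VII also promises the same outcome parameters for concurrent controls as for the EPR group. On this view, who rates and on which form is operational detail.

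It is fair that a discharge rating was probably intended. But the procedures section is where the protocol fixes what is measured and when. It names times for GOSE and leaves out the one that the primary outcome needs. An analysis plan cannot recover a rating that was never taken.

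Other points stand in part:

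- **Form.** Appendix B is badly extracted and some pages are not available, so a discharge field there cannot be ruled out. SF-36 has no visible field either, although the text schedules it. The conclusion rests on the text and not on the form.
- **Size.** The 20- and 10-point steps are simply 1/n and would apply to any misclassified subject. The wider ranges are unlikely under standard care: at 9% survival, the chance of at least 2 survivors among 5 is about 0.07, and of at least 3 among 10 about 0.05. Survival with EPR is unknown.
- **Consequence.** This is a 20-subject feasibility study, and the decision to proceed rests on complications and secondary endpoints. The protocol does not list the contents of the FDA reports. The first 5–10 cases are also discussed with the DSMB within 30 days, though no GOSE is specified there.

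These points limit the harm. They do not supply the missing rating.

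**Conclusion.** The concern holds. As written, the protocol defines its primary outcome at discharge by GOSE and schedules no GOSE at that time. Every subject discharged alive before month 6 lacks a planned primary-outcome rating, and no in-hospital death is affected. Each such subject leaves a group's rate uncertain by 20 points at 5 per group and by 10 points at 10 per group. The ranges assume that k subjects are unrated and that all others died in hospital; k is not given by the protocol.

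The damage is to the primary objective and its reporting, not to the stated criterion for proceeding. It should be corrected before enrolment continues, because a rating missed at discharge cannot be collected reliably later. Confidence is high for the text schedule and lower for the case report form.

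**What to change.** In Section XI (Procedures to assess efficacy) and Appendix B:

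1. Add a GOSE rating at hospital discharge for all EPR and concurrent control subjects discharged alive, naming the rater and the method, the same in both groups.
2. Record discharge date and status, and date of death if not already captured.
3. State that in-hospital death is scored GOSE 1.
4. For historical controls, state how the discharge GOSE is derived from records and how a record too thin to rate is handled and reported.
5. Keep the 6- and 12-month GOSE as secondary outcomes.

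The cut-off needs settling in the same amendment. It is above 5 in Section VII and in Procedures to assess efficacy, but 5 or above in the Section XI analysis text. That is a separate inconsistency, but until it is resolved a discharge GOSE of exactly 5 cannot be classified.

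The cost is one rating per live discharge, by the coordinator who already follows survivors, plus a few form fields and a written abstraction rule. Some historical records may prove unratable and would have to be reported as such.
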